9.2 Recruitment of infants born in the facility

All LBW infants will be screened at study facilities to determine their eligibility for the prospective cohort. LWB infants will be identified directly after birth in the same way as for the in-facility observations, and study staff will be notified (described above).

Some of the inclusion/exclusion criteria are best assessed through a brief chart check or discussion with clinicians. Once a LBW birth is identified, study staff will record on the screening instrument:

- Mother's age
- Congenital abnormalities, as defined in I/E criteria
- Infant critical or severe illness, as defined in I/E criteria

If the mother/infant pair is still eligible after these checks, then study staff will approach the woman to check the final criteria, which are whether she plans to leave the study area in the next six months. If she is still eligible, then we will progress to the consent process.

The target time for approaching a woman for the prospective cohort will be between 1 and 6 hours after the birth, but not within the first hour after the birth. There is a maximum time cutoff of 72 hours for recruitment to the prospective cohort; women can be enrolled at any time up to their discharge from the facility or 72 hours (whichever was first).

If an infant is born overnight when no study staff are present, then study staff will review the register or medical records when they arrive for their shift in the morning. Women can be approached for inclusion at that point. To avoid bias, we will pick the odd number admissions to select children for enrollment (1,3,5,7th admissions overnight) for inclusion.

6-month extension: This is not applicable see section 9.4

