Objectives	1: Understand the current practices and standard of care (SOC) for feeding LBW infants	2: Define and document the key outcomes (including growth, morbidity, and lack of success on MOM) for LBW infants under current practices	3: Assess the acceptability and feasibility of a system-level IYCF intervention and the proposed infant feeding options for LBW infants

To meet the first study objective of understanding practices, routine care and standard of care (SOC) for LBW infant feeding, we will use a mixed methods approach. First, we will conduct focus group discussions (FGD) with clinicians, mothers, family members, and religious leaders to understand current SOC and cultural practices around infant feeding. Second, we will enroll 35 mothers and up to 60 infants per site (approximately 35 pairs) for close in-facility feeding observation before discharge, focusing on the behaviors and interactions between mother, infant, and clinic staff regarding infant feeding. These feeding observations may be conducted in the neonatal care unit and Neonatal Intensive Care Unit (NICU), if applicable. Third, we will enroll and follow a prospective cohort of approximately 300 mothers and their LBW infants at each site. Caregivers of all LBW infants at each site will be approached for consent. All enrolled infants will be followed prospectively for up to six months through a regular schedule of clinic visits, and mothers will be regularly interviewed on their normal feeding practices and related topics. Anthropometric measurements will be taken across the six months of follow up. Fourth, a set of structured facility observations will assess the current patterns of infant feeds and maternal milk in the health facility to understand how infant feeds are currently provided under SOC.

For the 6-month extension:

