9.12 Sample size

The sample size will be as large as possible given constraints in time, recruitment rates, and budget. We do not plan to do any hypothesis testing using this observational data. The main statistical results will be point estimates and confidence intervals for certain rates, such as the percent of LBW infants who do not successfully breastfeed, require tube feeding, or the percent who develop certain conditions. The final sample size will determine the precision of the estimate, as shown in Figure 3. For example, with a sample of 250 infants, a true proportion of 5% can be estimated with precision of +/- 2.7%. The 95% confidence interval would be 2.3% to 7.7%.

Figure 3: Margin of error in estimation of a single proportion with a single sample

While we would like the precision of our estimates to be as high as possible, we have no statistical requirement for a particular number. Instead, we propose aiming for 350 enrolled mothers at each site, with an estimated final sample of 300 mothers in each site due to loss to follow up and withdrawal. This target will give a reasonable level of precision on the point estimates and appears logically achievable in the study period.

The sample of mothers will be different from that of infants due to multiple births; thus we expect up to 850 individuals be enrolled in the study if there are many sets of twins. We do expect twins to occur with some frequency in our samples, since we are selecting for LBW infants, and many multiples are LBW. The overall rates of multiple births in the general population are 7.2 per 1,000 births in India, 20.8 in Malawi, and 18.8 in Tanzania (Smits and Monden, 2011). We expect higher rates of multiples in our study population, so to be conservative, we double these estimates and assume our sample will include 14.4 multiples per 1,000 births in India, 41.6 in Malawi, and 37.6 in Tanzania. If these rates hold, and assuming both twins are eligible and enroll, then our sample of 300 women would include 304 infants in India, 313 infants in Malawi, and 311 infants in Tanzania. This will not greatly change the precision of the estimates shown for a sample of 300 in Figure 3.

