9.13 Response rates

The four study sites vary in annual birth volume and rate of LBW births (Table 6). The enrollment period for the prospective cohort will be approximately four months long (see Gantt chart), and each site expects

to have an estimated number of LBW babies born in that period. The table shows the response rates needed in each site in order to enroll 300 women into the cohort.

Table 6: Birth volume and response rates

Site	No. of study facilities	Annual birth volume		4-month study period	
		All births	LBW births (estimated)	LBW births (estimated)	Required response rate ¹
Dar es Salaam	3	35,997	5,550	1,850	16%
Lilongwe	2	20,000	1,280	427	70%
Karnataka	5	21,000	2,100	700	43%
Odisha	2	19,600	3,320	1,107	27%

¹ Percent of LBW births that need to be enrolled in order to achieve a total sample of 300; please note we may have a longer enrollment period than 4 months if required.

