9.20 Data analysis

As most of the quantitative data collected is being used for descriptive epidemiology of LBW infants, we will use means, medians and standard deviations to describe continuous variables. Categorical variables

will be analyzed with frequencies and proportions, as appropriate. Confidence intervals around all measures will be constructed to take any clustering into account.

For anthropometric analyses, we will use the INTERGROWTH charts to describe growth velocity and trajectories for the infants, including stunting (length-for-age z-score, LAZ), underweight (weight-for-age z-score, WAZ), and wasting (weight-for-length z-score, WLZ). To determine Z-scores, we will use the INTERGROWTH-21st standards for preterm infants (<37 weeks gestation), and the WHO postnatal growth standards for term infants (>37 weeks gestation) (Villar et al 2015).

Where possible, we will relate these anthropometric measures with reported infant feeding, using correlations for continuous variables or cross-tabulations of categorical variables. Any further analyses will be post-hoc and described separately.

6-month extension:

As with the original LIFE study, we will utilize mixed methods to fully understand the growth trajectories and care for LBW infants during the first 12 months of life. We will use the full cohort from 0 to 12 months of age to assess growth trajectories and velocities over time, evaluating the impact of complementary feeding (food types and timing) on infant anthropometrics, and assessing morbidities over time.

We will use descriptive methods for initial description of the LBW cohort with means, medians and standard deviations for continuous variables. Categorical variables will be analyzed with frequencies and proportions, as appropriate. Confidence intervals around all measures will be constructed to take any clustering into account.

For anthropometric analyses, for preterm infants we will use the INTERGROWTH-21st postnatal growth standards for preterm infants to describe growth velocity and trajectories for the infants up to 12 months of age, including stunting (length-for-age z-score, LAZ), underweight (weight-for-age z-score, WAZ), and wasting (weight-for-length z-score, WLZ). To determine Z-scores, we will use the INTERGROWTH-21st standards for preterm infants (<37 weeks gestation), and the WHO postnatal growth standards for term infants (>37 weeks gestation).

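### Section 9.2 takes only odd-numbered overnight admissions: this conflicts with approaching all LBW infants, under-represents night births if daytime approach is complete, and leaves the Table 6 response rates too low

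*Combined protocol and SAP*

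**What the plan says.** Section 4 describes the prospective cohort and states: "Caregivers of all LBW infants at each site will be approached for consent". Section 9.2 opens by screening all LBW infants at the study facilities. For overnight births, staff review the register or records in the morning, and mothers may be approached then. Recruitment stays open until discharge or 72 hours, whichever comes first. The section then adds: "To avoid bias, we will pick the odd number admissions to select children for enrollment (1,3,5,7th admissions overnight) for inclusion". It has no corresponding rule for births while staff are on shift. It does not say whether the numbering covers all admissions or only LBW births, whether mothers or infants are counted, or whether it restarts each night.

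The required response in Table 6 (Section 9.13) is defined as "Percent of LBW births that need to be enrolled in order to achieve a total sample of 300", with the qualification "please note we may have a longer enrollment period than 4 months if required". Section 9.12 sets the enrolment target: "we propose aiming for 350 enrolled mothers at each site". It also describes the output: "The main statistical results will be point estimates and confidence intervals for certain rates". Section 9.20 adds "Confidence intervals around all measures will be constructed to take any clustering into account" and does not mention selection weights.

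**The concern.** Site staff cannot approach every LBW caregiver and also take only alternate overnight admissions. The documents give no timing reason for the restriction, since the morning review and the 72-hour window already make overnight births reachable. The stated reason is to avoid bias. Yet if daytime births are all approached, night births enter with a lower probability than day births, which is the opposite of that aim. Section 8.4 recognises this kind of hazard when it rejects separate recruiting methods for premature and term infants.

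Two things are at stake. One is how well the site-level proportions represent LBW births at all hours. Section 11.1.1 notes that night births are left out of the in-facility observations, so the cohort is where they would be followed prospectively. The other is recruitment: the rule shrinks the pool that Table 6 treats as fully available. That effect does not depend on outcomes differing between day and night.

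**Working it through.** **Inputs from Table 6.** Annual LBW births and facilities: Dar es Salaam 5,550 and 3; Lilongwe 1,280 and 2; Karnataka 2,100 and 5; Odisha 3,320 and 2. Four-month LBW births: 1,850, 427, 700 and 1,107.

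**Assumptions, not in the documents.** Births are uniform over 24 hours and unstaffed nights last 8-12 hours, so the night share f is 1/3 to 1/2. Facilities within a site have equal volume, nightly counts are Poisson, and all daytime births are approached.

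**Reproducing Table 6.** 300/1,850 = 16.2%; 300/427 = 70.3%; 300/700 = 42.9%; 300/1,107 = 27.1%. These match the printed 16%, 70%, 43% and 27%.

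**Fraction of night LBW births kept, s.**
- Reading A, strict alternation: s = 0.5.
- Reading B, LBW births renumbered each night at each facility: with mean L = annual LBW / 365 / facilities × f, s = [L + (1 − e^(−2L))/2] / (2L). Starting at 1 on a short list keeps more than half. For Lilongwe at f = 1/2, L = 1,280/365/2 × 0.5 = 0.88 and s = 0.736.

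**Night share of those approached** = f·s / (f·s + 1 − f). Under A it is (1/6)/(5/6) = 20% at f = 1/3 and 0.25/0.75 = 33% at f = 1/2, at every site.

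**Response needed for 300** = 300 / [N(1 − f(1 − s))], where N is the four-month count. Paired values are for f = 1/3 and f = 1/2.

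| Site | s under B | Night share under B | Table 6 | Needed under A | Needed under B |
|---|---|---|---|---|---|
| Dar es Salaam | 0.643, 0.598 | 24.3%, 37.4% | 16.2% | 19.5%, 21.6% | 18.4%, 20.3% |
| Lilongwe | 0.795, 0.736 | 28.4%, 42.4% | 70.3% | 84.3%, 93.7% | 75.4%, 81.0% |
| Karnataka | 0.849, 0.797 | 29.8%, 44.4% | 42.9% | 51.4%, 57.1% | 45.1%, 47.7% |
| Odisha | 0.657, 0.609 | 24.7%, 37.8% | 27.1% | 32.5%, 36.1% | 30.6%, 33.7% |

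**Lilongwe, target of 350.** Without the rule, 350/427 = 82.0%. The remaining pool is 356 or 320 births under A, and 398 or 371 under B. The need becomes 98.4% or 109.3% (A) and 88.0% or 94.4% (B). At an unchanged response, the time needed is 4/(1 − f(1 − s)) months: 4.8 or 5.3 (A), 4.3 or 4.6 (B), against 4.0.

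**Possible outcome bias.** Bias = (night share approached − f) × day-night difference. For an assumed 10-point difference its size is 1.3-1.7 points under A (for example, (0.500 − 0.333) × 10 = 1.7) and 0.35-1.3 points under B. It is zero if rates do not differ. For comparison, the 95% margin at a 15% rate with n = 300 is 1.96 × √(0.15 × 0.85/300) = 4.0 points.

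**If daytime approach is incomplete.** With daytime capture d, the night share equals f when d = s. At f = 0.5, s = 0.6 and d = 0.4, it is 0.30/(0.30 + 0.20) = 60%, so nights would be over-represented.

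**The case against.** Several stronger readings are tempting, and the documents do not support them.

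- **That Section 9.2 contradicts itself.** Its general instruction reads: "If the mother/infant pair is still eligible after these checks, then study staff will approach the woman to check the final criteria". The odd-number sentence can fairly be read as a specific exception for unstaffed hours. Screening of all LBW infants also stays true if selection follows screening. The conflict is with Section 4.
- **That the estimates are biased.** No day-night difference in outcomes is given. The computed bias is below the sampling margin, and partial daytime approach could shrink or reverse the imbalance. Section 9.12 sets no required precision.
- **That imbalance could not be detected.** The 72-hour cutoff and the 1-6 hour approach target need the time of birth, so shift is probably derivable, although no tabulation by shift is planned.
- **That Section 9.20 commits to unweighted analysis.** It is silent on weights; the sentence quoted from it concerns clustering.
- **That Lilongwe is worst affected on every measure.** It has the largest rise in percentage points. In relative terms, reading A raises every site's need by the same factor, 1/(1 − f/2). Under reading B at f = 1/2 the factor is larger in Dar es Salaam (20.3/16.2 = 1.25) than in Lilongwe (81.0/70.3 = 1.15).
- **That the response figures are lower bounds.** Full eligibility is assumed, which understates the need. But Sections 9.1 and 9.3 also admit infants born elsewhere who present within 72 hours, which enlarges the pool.
- **That Lilongwe cannot reach its target.** The footnote permits longer enrolment.

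A workload reason for the rule is also conceivable, since each enrolment brings consent, questionnaires, repeated anthropometry and a gestational-age examination. The plan does not state one. These limits narrow the point, but they reconcile neither Section 9.2 with Section 4 nor Table 6 with the rule.

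**Conclusion.** The point holds in a limited form and should be corrected. The overnight rule conflicts with Section 4 and has no daytime counterpart. If daytime births are all approached as written, night births fall from an assumed 33-50% of births to 20-33% of those approached under strict alternation, or to 24-44% across sites with nightly renumbering of LBW births. A reader might infer that the results are therefore biased. That is possible but not shown, and the size is at most about 1.7 points per assumed 10-point day-night difference.

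The effect on recruitment is firmer, because it needs no difference in outcomes. Before any out-of-facility births are added, Lilongwe needs about 75-94% of LBW births rather than 70% for 300 mothers, and about 88-109% rather than 82% for 350. Given the footnote, this is a cost of roughly 0.3 to 1.3 months at an unchanged response, not a failure to recruit. All sizes rest on the assumed night share, equal facility volumes and complete daytime approach.

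**What to change.** In Section 9.2, delete the odd-number sentence. State that all eligible overnight LBW births are approached after the morning register review, within the existing limit of discharge or 72 hours. This agrees with Section 4 and leaves Table 6 as printed. Derive shift of birth from the recorded time of birth, and report the numbers eligible, approached and enrolled by shift.

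If workload requires sampling, apply one rule to day and night births alike, numbering eligible LBW mothers with multiples kept together, and restate Table 6 for the sampled pool. One-in-two sampling would leave about 427/2 ≈ 214 LBW births in Lilongwe over four months, below 300, so this fallback suits only sites with slack.

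The cost of the preferred change is the extra morning approaches, L(1 − s) per facility. The highest average is in Dar es Salaam under strict alternation at f = 1/2: 2.53 × 0.5 ≈ 1.3. This is a mean under equal facility volumes, so busy facilities and busy nights would see more. Each enrolment brings the usual consent and baseline work, but total enrolment is unchanged because the target is fixed.

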9.3 Recruitment of infants born outside the facility

In some sites, a subset of women give birth outside of a facility, typically at home, and bring their infants to the facility soon after birth. We would like to recruit these women into the prospective cohort, but will not be able to weigh their infants at birth. Given our definition of LBW, we will be recruiting infants who are at least 1500 g at birth and at most 2499 g at birth. However, infants typically lose weight quickly in the first days after birth, so these thresholds must be adjusted for women who arrive at facilities later.

We will recruit infants born outside the facility as long as they present at the facility within 72 hours of birth. We will evaluate for the inclusion criteria of LBW based on the elapsed time since birth and the baby's weight at first visit, according to Table 5.

The values in Table 5 are based on a review of several studies of weight loss among infants in the first few days, including weight curves for term vs. preterm infants, LBW vs. normal weight, and breastfed vs. formula fed (Bertini et al 2015; Flaherman et al 2015; Miller et al 2015; Anchieta et al 2004; Shaffer et al 1987; Christensen et al 2006). Weight curves for C-section births were excluded from consideration. In this literature, estimates of median weight loss at 72 hours range from -2% or -3% for term, normal weight, formula fed infants, to about -10% for LBW, exclusively breastfed infants. This range is large, and the variation in observed weights increases with each day of life, producing more uncertainty in the estimates by day three.

For these reasons, it will not be possible to know an infant's birthweight precisely based on weight at day three. Also, to support the field work for the study, we require a fairly simple algorithm for classifying infants who are a few days old as having been LBW at birth. Taking these considerations into account, we took approximations of median weight loss rates in the first three days from the literature, based on initial birthweight and other factors, and constructed the threshold weights presented in Table 5. We accept the imprecision of this algorithm for estimating birthweight in order to allow recruitment from the population of women who give birth at home.

Other than the weight criteria, all other inclusion/exclusion criteria, informed consent, and study activities for out of facility births will be identical to those for facility births.

6-month extension: This is not applicable see section 9.4

Table 5: Weight thresholds for inclusion of infants up to 72 hours old born outside the facility

Time since birth	Exactly	Weight thresholds for inclusion in study		Percent change from assumed birthweight	
		Minimum weight	Maximum weight	In minimum weight	In maximum weight
None	0 to < 6 hours	1500	< 2500	n/a	n/a
12 hours	6 hours to <18 hours	1483	< 2467	-1.3%	-1.1%
24 hours	18 hours to <30 hours	1467	< 2433	-2.7%	-2.2%
36 hours	30 hours to <42 hours	1450	< 2400	-4.0%	-3.3%
48 hours	42 hours to <54 hours	1433	< 2367	-5.3%	-4.4%
60 hours	54 hours to <66 hours	1417	< 2333	-6.7%	-5.6%
72 hours	66 hours to 72 hours	1400	< 2300	-8.0%	-6.7%

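### Do the swapped percentage columns in Table 5 cast doubt on the weight cut-offs for infants born outside a facility?

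*Combined protocol and SAP*

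**What the plan says.** Section 9.3 explains how the birthweight criterion applies to infants who were not weighed at birth. The target group is unchanged: "we will be recruiting infants who are at least 1500 g at birth and at most 2499 g at birth". Eligibility is judged from the time since birth and the "weight at first visit, according to Table 5".

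Table 5 is titled "Weight thresholds for inclusion of infants up to 72 hours old born outside the facility". Its first row sets the base: "None 0 to < 6 hours 1500 < 2500 n/a n/a". Six further rows, centred on 12 to 72 hours, lower both limits, ending at 1400 g and below 2300 g. Beside the grams stand two columns under the heading "Percent change from assumed birthweight", one for the minimum and one for the maximum weight. The 12-hour row, for example, reads "1483 < 2467 -1.3% -1.1" (minimum grams, maximum grams, minimum %, maximum %).

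On the source of the limits, the section says "we took approximations of median weight loss rates in the first three days from the literature, based on initial birthweight and other factors". It gives no loss figure for either limit. It adds: "We accept the imprecision of this algorithm for estimating birthweight".

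**The concern.** A percentage printed next to a cut-off should describe that cut-off, and here none of the 12 does. The reversal also changes the apparent assumption. As printed, the percentages say that the lightest eligible infants lose proportionally more weight (8.0% against 6.7% at 72 hours). The grams say the opposite.

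Table 5 is the only weight criterion for infants born outside a facility, and section 9.3 does not say whether grams or percentages came first. If the percentages were the intended input, the gram limits would be slightly wrong, and some infants near a limit could have been turned away in error. If only the labels are wrong, all that is at stake is an explanatory column.

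**Working it through.** **Inputs.** Base weights of 1500 g and 2500 g (first row of Table 5); the printed grams and percentages in the six adjusted rows; scale resolution of 10 g (Appendix A).

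**Step 1: percentages from the printed grams.** Loss % = 100 × (base − cut-off) / base. At 72 hours: (1500 − 1400)/1500 = 6.67% and (2500 − 2300)/2500 = 8.00%.

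**Step 2: percentages from even losses.** The grams fall in a straight line, by 100 g and 200 g over 72 hours. Before rounding, the loss at t hours is 100·t/72 g from 1500 g and 200·t/72 g from 2500 g. At 12 hours: 16.67/1500 = 1.11% and 33.33/2500 = 1.33%.

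All pairs are minimum / maximum, shown as losses:

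| Time | Printed grams | % from printed grams | % from even losses | Printed % |
|---|---|---|---|---|
| 12 h | 1483 / 2467 | 1.13 / 1.32 | 1.11 / 1.33 | 1.3 / 1.1 |
| 24 h | 1467 / 2433 | 2.20 / 2.68 | 2.22 / 2.67 | 2.7 / 2.2 |
| 36 h | 1450 / 2400 | 3.33 / 4.00 | 3.33 / 4.00 | 4.0 / 3.3 |
| 48 h | 1433 / 2367 | 4.47 / 5.32 | 4.44 / 5.33 | 5.3 / 4.4 |
| 60 h | 1417 / 2333 | 5.53 / 6.68 | 5.56 / 6.67 | 6.7 / 5.6 |
| 72 h | 1400 / 2300 | 6.67 / 8.00 | 6.67 / 8.00 | 8.0 / 6.7 |

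As labelled, no cell matches. With the two printed columns exchanged, all 12 match the even-loss figures to one decimal. Against the rounded grams, 10 of 12 match; the other two differ by 0.1 point (1433 g gives 4.5 against 4.4, and 1417 g gives 5.5 against 5.6). That pattern is what one expects if the percentages were computed from unrounded grams.

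**Step 3: other explanations at 72 hours.**
- Exchanged denominators: 100/2500 = 4.0% and 200/1500 = 13.3%. Neither is printed in that row.
- Current weight as denominator: 100/1400 = 7.14% and 200/2300 = 8.70%. Neither fits.
- 2499 g as the upper base: (2499 − 2300)/2499 = 7.96%, still not 6.7%.

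**Step 4: cut-offs if the percentages were meant as labelled.** Cut-off = base × (1 − printed %).

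| Time | Implied grams | Shift in minimum | Shift in maximum |
|---|---|---|---|
| 12 h | 1480.5 / 2472.5 | −2.5 g | +5.5 g |
| 24 h | 1459.5 / 2445 | −7.5 g | +12 g |
| 36 h | 1440 / 2417.5 | −10 g | +17.5 g |
| 48 h | 1420.5 / 2390 | −12.5 g | +23 g |
| 60 h | 1399.5 / 2360 | −17.5 g | +27 g |
| 72 h | 1380 / 2332.5 | −20 g | +32.5 g |

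Both 12-hour shifts and the 24-hour shift in the minimum are smaller than the 10 g scale step. In every row the printed window lies inside the implied one, so an infant enrolled under the printed limits would also qualify under the implied limits.

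**The case for a change.** The best argument for a change is that section 9.3 describes weight-loss rates as the starting material, so the percentages might be the source and the grams the error. The text also cites a median loss of about 10% at 72 hours for low-birthweight, exclusively breastfed infants, against 2% or 3% for term, normal-weight, formula-fed infants. That could be read as supporting a larger proportional loss at the lower limit, as the printed labels have it. Accepting imprecision in estimating birthweight does not excuse two columns that contradict each other.

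Part of this stands. The columns do conflict, nothing elsewhere in the document corrects them, and the intent is not formally stated. But the literature contrast does not settle the direction. It mixes birthweight with maturity and feeding type, and it sets low-birthweight infants against normal-weight ones rather than 1500 g against 2500 g. The numbers are far more telling. Percentages chosen independently would hardly equal 100/1500 and 200/2500, and their even fractions, in all 12 cells after one exchange of columns. The round figures in the table are the gram losses.

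Nor does the slip reach an analysis. The analysis section (9.20) does not use these percentages, and nothing in the document uses them to back-calculate birthweight.

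**Conclusion.** The inconsistency is real, but it is clerical. Table 5's two percentage columns are almost certainly transposed, by 0.2 points at 12 hours rising to 1.3 points at 72 hours, while the grams that staff apply are coherent. On that reading the effect on eligibility, enrolment and every planned estimate is zero.

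The conclusion rests on two assumptions. One is that the grams are the source, which the 12-of-12 match strongly supports but the text does not state. The other is that the column order in the typeset table is as read here, which is likely because both pairs of headings run minimum then maximum and all six rows agree. If the first assumption failed, the cost would be a small number of infants turned away within 2.5 to 20 g below the lower limit or 5.5 to 32.5 g above the upper one, confined to out-of-facility births first weighed at 6 to 72 hours. The document does not give the size of that group. No enrolled infant would become ineligible.

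When the document is next reissued, the sponsor can reconcile the grams and percentages, most likely by exchanging the two percentage columns, and confirm that the grams are as intended. That is housekeeping and does not alter the design or the analysis.
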